9.2.4 Visit 3: Week 1 (Day 8 ±1 day)

The following activities will be performed at Visit 3 (Week 1).

- Complete ODI assessment.
- Collect concomitant medication and therapy information.
 - Confirm use and amount of concomitant medication(s)/therapy(ies).
 - Assess use of restricted medication(s)/therapy(ies) for LDH.
- Review the subject daily diary and assess compliance.
- Collect vital signs.
- Record AEs.
- Perform neurological examination.
- Perform urine drug test for subjects prescribed hydrocodone/acetaminophen rescue.
- Collect blood sample for laboratory tests (hematology and chemistry panels).
- Provide instructions for recording daily pain assessment and rescue medication use.
- Distribute acetaminophen rescue, as described in Section 6.6.4.
- As applicable per Section 6.6.4, distribute hydrocodone/acetaminophen rescue medication. Discuss usage and counsel, as appropriate.
- Remind subject to avoid any strenuous activities.

9.2.5 Visits 4 and 5: Week 2 (Day 15 ±3 days) and Week 4 (Day 29 ±3 days)

The following activities will be performed at Visit 4 (Week 2) and Visit 5 (Week 4):

- Complete the ODI, SF-36, and PGIC assessments (SF-36 will not be performed at Visit 4).
- Collect concomitant medication and therapy information.

- Confirm use and amount of concomitant medication(s)/therapy(ies).
- Assess use of restricted medication(s)/therapy(ies) for LDH.
- Collect vital signs.
- Record AEs.
- Perform neurological examination.
- Perform urine drug test for subjects prescribed hydrocodone/acetaminophen rescue.
- Complete the CGIC assessment.
- Provide instructions for recording daily pain assessment and rescue medication use.
- Distribute acetaminophen rescue, as described in Section 6.6.4.
- As applicable per Section 6.6.4, distribute hydrocodone/acetaminophen rescue medication. Discuss usage and counsel, as appropriate.
- Remind subject to avoid any strenuous activities.

9.2.6 Visit 6: Week 6 (Day 43 ±7 days)

The following activities will be performed at Visit 6 (Week 6):

- Complete the ODI, SF-36, and PGIC assessments.
- Collect concomitant medication and therapy information.
 - Confirm use and amount of concomitant medication(s)/therapy(ies).
 - Assess use of restricted medication(s)/therapy(ies) for LDH.
- Collect vital signs.
- Record AEs.
- Perform neurological examination.
- Perform urine drug test for subjects prescribed hydrocodone/acetaminophen rescue.
- Complete the CGIC assessment.
- Collect blood sample for laboratory tests (hematology and chemistry panels).
- Provide instructions for recording daily pain assessment and rescue medication use.
- Provide subject education on accurate pain reporting and appropriate expectations of personal benefit in a clinical trial.
- Distribute acetaminophen rescue, as described in Section 6.6.4.
- As applicable per Section 6.6.4, distribute hydrocodone/acetaminophen rescue medication. Discuss usage and counsel, as appropriate.
- Remind subject to avoid any strenuous activities.

9.2.7 Visit 7: Week 13 (Day 92 -7, +14 days)

Contact will be made with the subject by telephone call (and/or other method) by a minimum of 14 days before this visit. The following activities will be performed at Visit 7 (Week 13):

- Complete the ODI, SF-36, PGIC, EQ-5D-5L, and WPAI assessments.
- Collect concomitant medication and therapy information.
 - Confirm use and amount of concomitant medication(s)/therapy(ies).
 - Assess use of restricted medication(s)/therapy(ies) for LDH.
- Collect vital signs.
- Record AEs.
- Perform neurological examination.
- Perform urine drug test for subjects prescribed hydrocodone/acetaminophen rescue.
- Complete the CGIC assessment.
- Collect blood sample for laboratory tests (hematology and chemistry panels).
- Determine whether there is treatment failure.
- Provide instructions for recording daily pain assessment and rescue medication use.
- Distribute acetaminophen rescue, as described in Section 6.6.4.
- As applicable per Section 6.6.4, distribute hydrocodone/acetaminophen rescue medication. Discuss usage and counsel, as appropriate.
- Remind subject to avoid any strenuous activities.
- Perform imaging tests (X-ray and MRI)*, assess the images, and transmit the images to the central independent image readers.

* If repeat imaging is needed, the window for imaging only will be extended by a maximum of an additional 7 days.

9.2.8 Visit 8: Week 26 (Day 183 ±14 days)

Contact will be made with the subject by telephone call (and/or other ways) by a minimum of 14 days before these visits. The following activities will be performed at Visit 8 (Week 26):

- Complete the ODI, SF-36, and PGIC assessments.
- Collect concomitant medication and therapy information.
 - Confirm use and amount of concomitant medication(s)/therapy(ies).
 - Assess use of restricted medication(s)/therapy(ies) for LDH.
- Collect vital signs.

- Record AEs.
- Perform neurological examination.
- Perform urine drug test for subjects prescribed hydrocodone/acetaminophen rescue.
- Complete the CGIC assessment.
- Provide instructions recording daily pain assessment and rescue medication use.
- Distribute acetaminophen rescue, as described in Section 6.6.4.
- As applicable per Section 6.6.4, distribute hydrocodone/acetaminophen rescue medication. Discuss usage and counsel, as appropriate.
- Remind subject to avoid any strenuous activities.

9.2.9 Visit 9: Week 39 (Day 274 ±14 days)

Contact will be made with the subject by telephone call (and/or other ways) by a minimum of 14 days before these visits. The following activities will be performed at Visit 9 (Week 39):

- Complete the ODI, SF-36, and PGIC assessments.
- Collect concomitant medication and therapy information.
 - Confirm use and amount of concomitant medication(s)/therapy(ies).
 - Assess use of restricted medication(s)/therapy(ies) for LDH.
- Collect vital signs.
- Record AEs.
- Perform neurological examination.
- Perform urine drug test for subjects prescribed hydrocodone/acetaminophen rescue.
- Complete the CGIC assessment.
- Provide instructions recording daily pain assessment and rescue medication use.
- Provide subject education on accurate pain reporting and appropriate expectations of personal benefit in a clinical trial.
- Distribute acetaminophen rescue, as described in Section 6.6.4.
- As applicable per Section 6.6.4, distribute hydrocodone/acetaminophen rescue medication. Discuss usage and counsel, as appropriate.
- Remind subject to avoid any strenuous activities.

9.2.10 Visit 10: Week 52 (Day 365 ±14 days)

Contact will be made with the subject by telephone call (and/or other ways) by a minimum of 14 days before these visits. The following activities will be performed at Visit 10 (Week 52):

Confidential
Version 7.0

- Complete the ODI, SF-36, PGIC, EQ-5D-5L, and WPAI assessments
- Collect concomitant medication and therapy information.
 - Confirm use and amount of concomitant medication(s)/therapy(ies).
 - Assess use of restricted medication(s)/therapy(ies) for LDH.
- Collect vital signs.
- Record AEs.
- Record occurrence of any lumbar surgery.
- Perform neurological examination.
- Complete the CGIC assessment.
- Determine whether there is treatment failure.
- Collect or account for any remaining rescue medication.
- Perform imaging tests (X-ray and MRI) *, assess the images, and transmit the images to the central independent image readers.
 - * If repeat imaging is needed, the window for imaging will be extended by a maximum of an additional 7 days.

9.2.11 Discontinuation Visit

Subjects who discontinue early from the study will be asked to complete a discontinuation visit. The following activities will be performed at the discontinuation visit:

- Complete the ODI, SF-36, PGIC, EQ-5D-5L, and WPAI assessments
- Collect concomitant medication and therapy information.
 - Confirm use and amount of concomitant medication(s)/therapy(ies).
 - Assess use of restricted medication(s)/therapy(ies) for LDH.
- Collect vital signs.
- Record AEs.
- Record occurrence of any lumbar surgery.
- Perform neurological examination.
- Complete the CGIC assessment.
- Collect blood sample for laboratory tests (blood for hematology and chemistry panels)*.
- Determine whether there is treatment failure.
- Collect or account for any remaining rescue medication.

- Perform imaging tests (X-ray and MRI), assess the images, and transmit the images to the central independent image readers
 - * If the subject discontinues prior to or within Week 13.

Subjects who discontinue early from the study will also be followed until Week 52 for the occurrence of any lumbar surgery.

9.2.12 Unscheduled Visit

In the event the investigator needs to conduct follow-up assessments to evaluate an AE, the following safety assessments may be performed on an unscheduled basis:

- Collect vital signs.
- Collect blood sample for laboratory tests (hematology and chemistry panels).
- Perform imaging tests (X-ray and MRI), assess the images, and transmit the images to the central independent image readers.

9.3 Background and Demographic Characteristics

9.3.1 Demographics

For subject demographics, the following information will be documented at the screening visit.

- Date of birth
- Sex [Male, Female]
- Race [American Indian or Alaska Native, Asian, Black or African American, Native Hawaiian or Other Pacific Islander, White, Other]
- Ethnicity [Hispanic or Latino, Not Hispanic or Latino]
- Height
- Weight
- Smoking history [Never smoked, Past smoker, Current smoker]
- Occupation [Heavy labor, Light labor]

9.3.2 History of Lumbar Disc Herniation

For disease history of LDH, the following information will be documented at the screening visit.

- Date of Diagnosis
- Herniation Site [L4-L5, L5-S1*]
- Location of Herniation [Left, Right]

- Location of Radicular Leg Pain [Left, Right]
- Date of Onset of Current Radicular Leg Pain
- Ongoing Low Back Pain Caused by Herniation [Yes, No]
*including L5-L6

9.3.3 Medical History

For the documentation of medical history, any previous and concomitant diseases within the last 26 weeks and any significant medical history occurring before the time of informed consent will be investigated at the screening visit. The medical history will be obtained by interviewing the subject and/or by inspecting his/her medical records.

A brief history of the following treatments, if they have been used, will be recorded:

- Medications used for LDH in the 26 weeks before the time of informed consent:
Name of medication, Usage, Frequency, Route, Start date, End date
- Physical therapies used for LDH in the 26 weeks before the time of informed consent:
Name of therapy, Frequency, Start date, End date
- Block procedure used for LDH: Name of procedure, Date

9.4 Concomitant Medications/Therapies

9.4.1 Concomitant Medications

Investigators will record the following information for all medications used concomitantly during the period from 6 weeks prior to informed consent to 52 weeks after administration, or until the time of discontinuation.

- Name of medication
- Dose
- Route of administration
- Frequency
- Start date / End date
- Indication [LDH, Adverse event, Medical history, Other]

9.4.2 Concomitant Therapies

Investigators will record the following information for therapies used concomitantly for treatment of LDH during the period from time of informed consent to 52 weeks after administration, or until the time of discontinuation.

- Name of therapy

- Frequency
- Start date / End date

9.5 Efficacy Assessments

9.5.1 Pain Intensity

- Assessment Points: Daily from screening until Week 52
- Item: Worst leg pain and worst low back pain during the past 24 hours assessed by 100 mm VAS
- Method: The 100 mm VAS pain assessment tool will be used to measure pain intensity. At the screening visit, the investigator will provide a daily diary and instruct subjects to record daily the pain intensity from LDH over the last 24 hours basically before going to bed.

9.5.2 Oswestry Disability Index

- Assessment Points: Week 0, 1, 2, 4, 6, 13, 26, 39, and 52, and discontinuation visit
- Item: ODI, Version 2.1a
- Method: Investigator will have subjects answer the ODI questionnaire at each listed visit.

9.5.3 36-item Short Form Survey

- Assessment Points: Week 0, 4, 6, 13, 26, 39, and 52, and discontinuation visit
- Item: SF-36 v2 Standard, US Version 2.0
- Method: Investigator will have subjects answer the SF-36 questionnaire at each listed visit.

9.5.4 EuroQol Group 5-Dimension Quality of Life Instrument

- Assessment Points: Week 0, 13, and 52, and discontinuation visit
- Item: EQ-5D-5L
- Method: Investigators will have subjects answer the EQ-5D-5L questionnaire at each listed visit.

9.5.5 Patient Global Impression of Change

- Assessment Points: Week 2, 4, 6, 13, 26, 39, and 52, and discontinuation visit
- Item: PGIC questionnaire

- Method: Investigators will have subjects answer the PGIC questionnaire at each listed visit.

9.5.6 Clinical Global Impression of Change

- Assessment Points: Week 2, 4, 6, 13, 26, 39, and 52, and discontinuation visit
- Item: CGIC questionnaire
- Method: Investigators will answer the CGIC questionnaire based on subject's condition at each listed visit.

9.5.7 Work Productivity and Activity Impairment

- Assessment Points: Week 0, 13, and 52, and discontinuation visit
- Item: Work Productivity and Activity Impairment Questionnaire: Pain related to Lumbo-sacral Radiculopathy V1.0 (WPAI-PLR, referred to as WPAI)
- Method: Investigators will have subjects answer the WPAI questionnaire at each listed visit.

9.5.8 Rescue Medication Use

- Assessment Points: Daily from screening until Week 52
- Item: Amount of rescue medication used
- Method: At the screening visit, the investigator will provide a daily diary and instruct subjects to record daily the amount of rescue medication over the last 24 hours, basically before going to bed. The investigator will clarify the requirements for timing of opioid rescue as it relates to the other study assessments.

9.5.9 Neurologic Status

- Assessment Points: All Visits
- Item: SLR test [Positive ($\leq 70^\circ$) or Negative ($> 70^\circ$)], sensation [Yes, No for existence of hypoesthesia], muscle strength [Yes, No for existence of muscle weakness], and deep tendon reflex [Yes, No for existence of hyporeflexia]
- Method: Neurological examinations will be performed by the investigator, and the results will be documented.

9.5.10 Treatment Failure

- Assessment Points: Week 13 and 52, and discontinuation visit

- Item: Treatment Failure [Yes, No], Reason [Concomitant medication use, Safety reason, Efficacy reason, Poor response, Increase of vertebral body angle, Increase of vertebral body translation]
- Method: Investigator will record the condition of and information about treatment failure. Treatment failure is defined in Section 8.1.3.

9.5.11 Disc and Herniation Volumes

- Assessment Points: Screening visit, Week 13, and 52, and discontinuation visit
- Item: Disc volume, Herniation volume
- Method: Disc and herniation volumes will be assessed with MRI by a central imaging facility. The investigator or site staff will collect the images and transmit them to the central imaging facility, according to a separately distributed manual.

9.5.12 Post-treatment Surgery for Lumbar Disc Herniation at Target Level

- Assessment Point: Week 52 (subjects who discontinued the study will be also followed until 52 weeks after injection)
- Item: Occurrence of lumbar disc surgery for LDH [Yes, No], Date of surgery
- Method: At 52 weeks after injection, investigators will collect information on the occurrence of post-treatment surgery for treatment of LDH at the same level of administration of the investigational product, including for subjects who discontinued from the study.

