5.3 Post-treatment Surgery Follow-up for Withdrawn Subjects

Subjects withdrawn from the study will be followed by investigators until 52 weeks after injection to gather data about post-treatment surgery. Information about post-treatment

surgery will be collected for following surgery types:

- Post-treatment surgery for treatment of LDH at the same level of administration of the investigational product;
- Post-treatment surgery for treatment of LDH at a different level than administration of the investigational product; and
- Post-treatment lumbar surgery not for treatment of LDH.

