5. STUDY SUBJECTS

5.1 Disposition of Subjects

A disposition table of subjects will include the number and percentage of subjects for the following categories: subjects screened, subjects randomized, subjects treated (safety sample), subjects in the mITT sample, subjects in the PP sample, subjects completing through Week 13, subjects completed study, and subjects discontinued from the study. A separate summary of discontinuations through Week 13 will also be presented. All percentages will be based on the number of subjects randomized (with the exception of subjects screened). Additionally, the number of subjects excluded from each population and reason for exclusion will be presented overall and by site.

The reasons for study discontinuation will also be summarized in this table. The reason for discontinuation may include any of the following: lack of efficacy, death, adverse event, lost to follow-up, failure to meet randomization criteria, protocol violation, physician decision, withdrawal by subject, pregnancy, study terminated by sponsor, and other. Subjects that do not complete the study will be flagged if they had early termination due to confirmed COVID-19, early termination at site discretion due to COVID-19, or early termination at subject discretion due to COVID-19; this will be summarized with the number and percentage of subjects in each category. Only the primary reason for study discontinuation will be recorded for a given subject.

The number and percentage of subjects attending each visit will be summarized. Due to the COVID-19 pandemic, visits could be in-person, remote or a combination; the reason for a remote visit could be due to the subject having confirmed COVID-19, at site discretion due to COVID-19, at subject discretion due to COVID-19 or other reasons. Likewise visits may have been missed or canceled due to the subject having confirmed COVID-19, at site discretion due to COVID-19, at subject discretion due to COVID-19 or other reasons. Additionally, individual assessments may have been omitted due to COVID-19; this is recorded on the CRF.

The type of visit (in-person, remote, or combination), the reason for remote visits, the reason visits were missed and assessments missed due to COVID-19 will be summarized with counts and percentages for each visit and treatment group.

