7.3.2.2 Sensitivity analyses

As a sensitivity analysis, missing data for participants in the mITT population will be imputed via MI. Twenty repeats of the imputation will be performed using Markov Chain Monte Carlo (MCMC) assuming non-monotone missing. Where the subject was discontinued due to lack of efficacy, due to an AE (with the exception of COVID-19), the subject has met the criteria for treatment failure as described in Section 7.3.3.4, or the subject's values are censored due to a prohibited therapy as described in Section 7.3.2.1, missing values will be imputed drawing from the baseline values, conditioned on the non-missing post-baseline values, of all participants in the mITT population under the assumption that they are missing not at random (MNAR); duration of leg pain will be included as a covariate.

If the study medication was discontinued for any other reason, values will be imputed within treatment group using MI under the assumption that they are missing at random (MAR) with covariates for duration of leg pain, and the weekly average worst leg pain score recorded at each time point (including baseline). The MAR approach will also be applied for sporadic missing values (prior to discontinuation). Values missing due to COVID-19, whether the result of early termination or sporadic missing values, are assumed MAR and unrelated to the endpoint of the weekly average VAS worst leg pain.

Data will be imputed for the full set of visits as described above and the same output will be used as a sensitivity for both the primary at Week 13 and the secondary endpoint at Week 52.

The MMRM analysis as described for the primary will be repeated for each of the 20 sets of data and combined using SAS PROC MIANALYZE. See Appendix [13.2](#) for the list of random seeds.

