11. CHANGES TO THE ANALYSES PLANNED IN THE PROTOCOL

The protocol-specified MI sensitivity analysis to the primary did not include consideration for subject data that is set to missing following a prohibited procedure; this has been included among the study outcomes that use the baseline distribution for imputation.

The multiple comparison algorithm has been updated to do a more straightforward serial gatekeeping approach.

The recurrence of LDH endpoint in the protocol references one of the treatment failure criteria; because this criteria was nested in other requirements that would conflict with the recurrence of LDH criteria, the text was updated to focus on only the applicable items. Additionally, surgical intervention was removed as a criteria and the symptom criteria were clarified.

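### LDH surgery after Week 13 that is learned of only after withdrawal meets no clear MNAR trigger in the SAP 7.3.2.2 imputation, which matters mainly for Week 52 leg pain

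*Protocol*

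**What the plan says.** **Surgery follow-up.** Protocol 5.3: "Subjects withdrawn from the study will be followed by investigators until 52 weeks after injection", in order to learn of lumbar surgery. Protocol 9.5.12 repeats this for the injected level ("subjects who discontinued the study will be also followed until 52 weeks after injection") and collects a yes/no answer and the date.

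**Imputation rule.** SAP 7.3.2.2 fills missing leg pain scores from the mITT baseline distribution, conditional on the subject's observed post-baseline scores, in four situations:

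1. discontinuation for lack of efficacy;
2. discontinuation for an adverse event other than COVID-19;
3. "the subject has met the criteria for treatment failure as described in Section 7.3.3.4";
4. the subject's "values are censored due to a prohibited therapy as described in Section 7.3.2.1".

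For the rest: "If the study medication was discontinued for any other reason, values will be imputed within treatment group using MI", assuming missing at random (MAR).

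**Definitions behind triggers 3 and 4.** Treatment failure (SAP 7.3.3.4) covers conditions arising up to Week 13, among them starting a prohibited therapy. Protocol 6.7.1 lists lumbar operation for LDH symptoms as prohibited throughout. SAP 7.3.2.1 drops diary scores on days after a lumbar operation, percutaneous nucleotomy or intradiscal therapy. SAP 11 explains that the sensitivity analysis was extended to "subject data that is set to missing following a prohibited procedure".

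**Reason coding.** SAP 5.1: "Only the primary reason for study discontinuation will be recorded for a given subject".

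**Use of the imputed data.** One set of imputations serves leg pain at Week 13 and Week 52. SAP 7.3.3.2 applies the same method to the other key secondary endpoints. In SAP 7.3.4, Week 52 leg pain is second in the testing sequence and gates herniation volume and ODI.

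**The concern.** The SAP treats a lumbar operation as an outcome that should not be credited with the course of comparable unoperated subjects, and it extended the protocol's plan to say so. The protocol then keeps collecting operations after withdrawal. The imputation rule does not connect the two. An operated subject whose single recorded reason is, for example, withdrawal by subject or physician decision can fall under the catch-all MAR rule although the database holds the surgery and its date.

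At stake is the credibility of one analysis. This imputation is the only planned departure from MAR for the continuous primary and key secondary endpoints. Week 52 is where there has been most time to be operated on after leaving, and the Week 52 leg pain test decides whether the next two key secondaries can be tested.

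**Working it through.** **Step 1. Reproduce the plan's own figure, to fix the scale.** Inputs from Protocol 11.8.6 and SAP 2.6: difference 12 mm, SD 30 mm, two-sided 5%, power 90%, dropout 15%.

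- n per arm = 2 × (1.960 + 1.282)² × 30² / 12² = 131.4, so 132. Allowing for dropout, 132 / 0.85 = 155.3, so 156.
- The exact t-test gives 133, then 133 / 0.85 = 156.5, so 157 per arm (314 in all).
- Both agree with the planned 160 per arm within 3%.
- With 160 × 0.85 = 136 observed per arm, SE of the difference = 30 × √(2/136) = 3.64 mm.

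**Step 2. Run each kind of surgery through the four triggers.**

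| Case | Trigger met | Imputation |
|---|---|---|
| A. Surgery while the diary continues, any week | 4: later scores are censored | MNAR |
| B. Discontinued for lack of efficacy or a non-COVID AE, then surgery | 1 or 2 | MNAR |
| C. Withdrawn for another reason, surgery by Week 13 | 3: a prohibited therapy was started (SAP 7.3.3.4, Protocol 6.7.1) | MNAR as written |
| D. Withdrawn for another reason, no treatment failure by Week 13, surgery after Week 13 | none clearly | MAR within arm |

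In case C one practical doubt remains. Protocol 9.5.10 records treatment failure only at Week 13, Week 52 and the discontinuation visit, and the SAP does not say that surgery learned of later updates that status.

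In case D, trigger 3 has expired. Trigger 4 works by removing diary scores, and a withdrawn subject has none to remove. Protocol 9.4.2 stops recording concomitant therapies at discontinuation, so the operation appears only in the separate surgery follow-up, which SAP 7.3.2.2 does not mention.

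**Step 3. Which time points can move.** Surgery after Week 13 cannot change the status of a Week 13 value if the rule is applied to visits on or after the procedure date, and surgery by Week 13 is case C. What remains is mainly leg pain at Week 52. The Week 52 results that SAP 7.3.3.2 reports for ODI and herniation volume share the gap but are outside the testing sequence.

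**Step 4. Size, on assumptions.** Shift in one arm's mean = k × d / 160, where k is the number of case D subjects in that arm and d is the gap between a MAR value and an MNAR value. The documents give no rate of surgery after withdrawal, so k = 1, 3, 5 is assumed. For d, the Japanese phase 3 mean changes at Week 13 (Protocol 1.2.2.1: −34.3 mm placebo, −49.5 mm at 1.25 U) stand in for a MAR value, set against zero change. An assumed d of 15 mm represents a subject whose observed scores were already poor.

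| k | d = 15 | d = 34.3 | d = 49.5 | range in units of 3.64 mm |
|---|---|---|---|---|
| 1 | 0.09 | 0.21 | 0.31 | 0.03 to 0.09 |
| 3 | 0.28 | 0.64 | 0.93 | 0.08 to 0.26 |
| 5 | 0.47 | 1.07 | 1.55 | 0.13 to 0.43 |

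The larger values of d overstate the gap, because the MNAR draws are conditioned on observed scores and need not sit at zero change. The inputs are Week 13 figures used as a yardstick: the protocol gives Week 52 pain levels for that study but no baseline, so a Week 52 change cannot be derived.

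**The case against.** **Trigger 4 can be read more widely.** SAP 7.3.2.1 excludes days after an operation without requiring that the subject still be in the study. Protocol 6.7.1 also has subjects discontinued when they are to receive a prohibited therapy, so on the narrow reading the trigger would seldom apply. This has force. But both SAP 7.3.2.2 and SAP 11 speak of values that are censored or set to missing, which presupposes values. The fair description is that no trigger is clearly met, and two programmers could implement it differently.

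**Few subjects qualify.** Protocol 5.1 places LDH surgery under poor response, which points to the lack-of-efficacy reason. A case D subject must leave for something else, avoid treatment failure by Week 13, be operated on later, and still be reachable; SAP 8.3.4 bases its surgery percentages on subjects successfully contacted. This stands, and it is why the effect is probably small.

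**Other analyses count these subjects unfavourably.** Missing values are non-response in the 30% and 50% leg pain comparisons and in the cumulative distribution plots, and surgery has its own log-rank and Fisher tests. True, but none of these is a sensitivity analysis for the mean difference at Week 52.

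**A stronger inference a reader might draw** is that surgery does not trigger MNAR imputation at all, or that the Week 13 primary result is exposed. The documents do not support either. Cases A to C are covered as written, and the primary MMRM does not use this imputation.

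**Conclusion.** The point holds in a narrow form. For a subject withdrawn for a reason outside triggers 1 and 2, without treatment failure by Week 13 and operated on for LDH after Week 13, SAP 7.3.2.2 has no clear MNAR trigger, and the catch-all MAR rule applies. The same operation during diary collection is handled the opposite way.

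The consequence is mainly for the Week 52 worst leg pain sensitivity analysis. The primary MMRM is untouched, and Week 13 leg pain, herniation volume and ODI are essentially unaffected.

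On 1 to 5 assumed subjects in one arm of 160, the arm mean moves by about 0.1 to 1.5 mm. That is up to 0.43 of the 3.64 mm SE, with the upper end overstated. A reader might infer that the gap favours SI-6603, but the documents do not show this. If such surgery is commoner in the SI-6603 arm, MAR imputation flatters the product; if commoner in the control arm, it flatters control and is conservative. Neither the number of subjects nor the direction is known. This is a cheap improvement to a sensitivity analysis and has no bearing on sample size.

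**What to change.** Add to SAP 7.3.2.2, and carry into 7.3.3.2:

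- Any lumbar operation, percutaneous nucleotomy or intradiscal therapy for LDH recorded up to Week 52, including one learned of after withdrawal (Protocol 5.3, 9.5.12), sends missing values at visits on or after the procedure date to the MNAR rule, whatever discontinuation reason is recorded.
- Surgery by Week 13 learned of after withdrawal counts as meeting the treatment-failure criteria of SAP 7.3.3.4 for this purpose.

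This follows the intent already stated in SAP 11. The cost is one extra data merge, using surgery dates that the log-rank analysis in SAP 7.3.3.3 already needs, and a sensitivity estimate that may be slightly less favourable. The follow-up after withdrawal is framed around surgery, so an intradiscal therapy would be caught only where it happens to be recorded.
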